9.3.3 ANALYSIS OF THE SECONDARY ENDPOINT(S)

Secondary efficacy endpoints for the study are given by a set of continuous/count measures observed at days 4, 10 and 21 (i.e., components of the RAS and blood biomarkers indicative of pro-inflammatory and coagulation disturbances, circulating T cell (CD4 and CD8), NK cell, and monocytes). A shift in distribution location parameter will be tested for the group companion, using two sample t-test or the Wilcoxon rank-sum test selected upon the outcome distributions. Additionally, longitudinal secondary outcomes obtained at baseline (day 1), days 4, 10, and 21 will be analyzed using generalized mixed effect models and together with a proper link function (i.e., identity, log, etc.). In those models, days: treatment interactions, will be tested for the differences in trajectories. Covariate adjustments will be applied if required.

AEs are categorical data. AEs will be summarized as frequencies and percentages within telmisartan and placebo groups. Chi-squared test or Fisher's exact test will be used to test for differences in proportions between two groups.

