6.4.11 SCHEDULE OF EVENTS TABLE

Schedule of Events	Phone Screen	Entry (Day 1)	Day 4	Day 10	Day 21
Review COVID-19 symptoms and date of COVID-19 testing; Obtain Demographics, verbal Ht and Wt and Co-Morbid Medical History; Obtain Verbal Informed Consent	x				
Update current illness and confirm eligibility for study; verify signing of Informed Consent		x			
Complete Symptom Scale and Clinical Status		x	x	x	x
Vital Signs (Temp, Pulse, BP, Resp Rate, O ₂ sat)		x	x	x	x
Pregnancy test (except in post-menopausal state)		x	x*	x*	x*
Oro-pharyngeal Swab		x	x	x	x
Safety Labs (CBC with diff, chem, hsCRP, LDH) [10 ml]		x	x	x	x
RESEARCH Bloods including for RAS assessment (volume to be drawn) [25 ml]		x	x	x	x
TOTAL BLOOD VOLUME (ml)		35	35	35	35

*If possibility of pregnancy is solicited from participant

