9.3 DESCRIPTION OF STATISTICAL METHODS

9.3.1 GENERAL APPROACH

This is a prospective, randomized, double-blind 3-week study of telmisartan vs placebo in symptomatic individuals diagnosed with COVID-19 disease. Subjects will be randomized 1:1 to receive telmisartan vs placebo for 3 weeks (21 days). A block randomization will be applied to ensure the balance of participant numbers and baseline severity between treatments.

The baseline characteristics of participants will be summarized by descriptive statistics and compared between the two groups to check any imbalance. The primary efficacy endpoint for the study is an ordinal outcome corresponding to the maximum clinical status of the study subject. The proportional odds model and logistic regression techniques will be applied to compare the ordinal outcome between treatments, based on odds ratios. There are several secondary efficacy endpoints defined for the study. For those measures, averages and rates will be compared between groups, appropriately. Longitudinal mixed-effects models will be utilized to handle longitudinal outcome measures observed at days 1, 4, 10, and 21. The covariate use in regression models will be limited due to the relatively small sample size. Tests of normality will be performed on continuous data and transformation applied where applicable. Type-I error for hypothesis tests will be fixed at 5% nominal level. All efficacy and safety estimates (e.g.

average and proportions) will be provided with 95% confidence intervals (95% CI). The multiplicity error in exploratory analyses will be corrected via the false discovery rate. All efforts will be taken to minimize loss-to-follow-up. However, small amounts of missing data may occur. In such cases, participants without final outcome data will be excluded from the analysis. Sensitivity analysis with multiple imputations will be performed for confirming results. Statistical analyses will be performed using the R software 3.5.1 version.

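### The direct arm comparison of RAS and biomarker levels at days 4, 10 and 21 does not adjust for the same analyte's pre-dose day 1 level, and the added mixed model recovers only part of the lost precision

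*Combined protocol and SAP*

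**What the plan says.** Section 9.3.3 describes the secondary efficacy endpoints as "a set of continuous/count measures observed at days 4, 10 and 21" and tests for a location shift between arms "using two sample t-test or the Wilcoxon rank-sum test selected upon the outcome distributions". That comparison has no baseline term and no change score.

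A second analysis follows: "longitudinal secondary outcomes obtained at baseline (day 1), days 4, 10, and 21 will be analyzed using generalized mixed effect models". Its test is specified as "In those models, days: treatment interactions, will be tested for the differences in trajectories". The section ends with "Covariate adjustments will be applied if required", which names no covariate and gives no trigger. Section 9.3.1 adds: "The covariate use in regression models will be limited due to the relatively small sample size". Neither section says which of the two analyses is the main one.

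The Schedule of Events (6.4.11) marks research bloods at entry (day 1), day 4, day 10 and day 21. Under 6.4.6 the entry blood is drawn at the visit and the first dose is taken after the participant gets home, so the day 1 level is a pre-treatment value.

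**The concern.** With 20 per arm, stable differences between people in an analyte's level make up part of the error in a raw two-group comparison. A pre-dose value of the same analyte explains some of that variation whenever day 1 and follow-up levels correlate. Using it as a covariate also removes the effect of chance imbalance at entry.

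The study rationale presents the RAS and biomarker data as important preliminary evidence on pathogenesis. A wider confidence interval than the collected data require is therefore a real, if modest, loss. The question is whether the mixed model already makes it good.

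**Working it through.** **Inputs.** From 9.4: 20 per arm and a standardised effect d = 0.9. From 9.3.1: 5% type I error. Assumed: two-sided tests (the plan states one-sided only for the primary endpoint), complete data, equal SD at day 1 and follow-up, and a day 1 to follow-up correlation ρ, which the documents do not give.

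**Step 1: reproduce the plan's figure.** Section 9.4 claims more than 80% power for a t-test at d = 0.9. The noncentrality is d·√(n/2) = 0.9 × √10 = 2.846. The normal approximation gives Φ(2.846 − 1.960) = Φ(0.886) = 0.812. The exact noncentral t with 38 df gives 0.792. The claim therefore reproduces under the normal approximation and is just under 80% exactly. The exact value is used below.

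**Step 2: day 1 as covariate.** The residual SD is multiplied by √(1 − ρ²), so the noncentrality is 2.846/√(1 − ρ²) with 37 df:
- ρ = 0.3: 2.846/0.954 = 2.98
- ρ = 0.5: 2.846/0.866 = 3.29
- ρ = 0.7: 2.846/0.714 = 3.99

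**Step 3: the planned mixed model.** For the primary endpoint's longitudinal model, 9.3.2 lists treatment, days and their interaction as fixed effects. If 9.3.3 is built the same way with day categorical, each visit's interaction contrast is the arm difference in change from day 1. The SD is then multiplied by √(2(1 − ρ)), and the noncentrality is 2.846/√(2(1 − ρ)) with 38 df:
- ρ = 0.3: 2.846/1.183 = 2.41
- ρ = 0.5: 2.846/1.000 = 2.85
- ρ = 0.7: 2.846/0.775 = 3.67

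**Step 4: power.** The last column is the adjusted analysis minus the better of the two planned routes, in percentage points.

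| ρ (assumed) | Raw test | Change contrast | Day 1-adjusted | Gain |
|---|---|---|---|---|
| 0 | 0.792 | 0.501 | 0.791 | −0.1 |
| 0.2 | 0.792 | 0.592 | 0.807 | 1.5 |
| 0.3 | 0.792 | 0.650 | 0.828 | 3.6 |
| 0.4 | 0.792 | 0.716 | 0.856 | 6.4 |
| 0.5 | 0.792 | 0.792 | 0.893 | 10.1 |
| 0.6 | 0.792 | 0.873 | 0.934 | 6.1 |
| 0.7 | 0.792 | 0.947 | 0.973 | 2.6 |
| 0.8 | 0.792 | 0.992 | 0.996 | 0.4 |

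**Step 5: simulation check.** With 40,000 replicates, the raw / change / adjusted powers were 0.790 / 0.648 / 0.816 at ρ = 0.3, 0.790 / 0.793 / 0.883 at 0.5, and 0.789 / 0.946 / 0.967 at 0.7. The adjusted figures are about one point below the formula, so the simulated gains are 2.6, 9.0 and 2.1 points.

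**Step 6: the same result as detectable effect.** At 80% power the detectable d is 0.91 for the raw test. With day 1 adjustment it is 0.87, 0.79 and 0.65 at ρ = 0.3, 0.5 and 0.7. For the change contrast it is 1.08, 0.91 and 0.70.

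**The case against.** The strongest reply is that the plan already uses day 1. The sentence after the t-test/Wilcoxon comparison puts day 1 into a mixed model, and covariate adjustment is allowed. This stands against a reader who infers that the trial ignores or discards its baseline samples: the documents do not support that. It does not remove the narrower point. Treating day 1 as an outcome with its own arm difference yields a change contrast, which below ρ = 0.5 is weaker than the raw test. A conditional, unnamed adjustment is also not a commitment to use the day 1 analyte.

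A second reply is that setting 0.79 against 0.97 at ρ = 0.7 overstates the loss, because the planned change contrast already reaches 0.95 there. That is correct, and the gain has to be read against the better planned route.

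Third, ρ is unknown. Entry sets no limit on time since symptom onset, and the 72-hour test window can be waived (5.1), so a weak correlation between day 1 and day 21 cannot be excluded. That stands, and in that case the gain is small.

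A reader might also object to choosing the test from the observed distribution, together with the statement in 9.3.1: "Tests of normality will be performed on continuous data and transformation applied where applicable". No material harm was shown. In a log-normal simulation the pretest route had 77% power against 79% for a log-scale t-test, with type I error of 0.051 and 0.053.

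**Conclusion.** The point holds as a matter of efficiency. The direct comparison omits the pre-dose level, and the additional mixed model makes good only part of the loss. By formula, day 1 adjustment gains about 3 to 10 power points over the better planned route for ρ between 0.3 and 0.7, with the peak near 0.5. At ρ = 0 it costs 0.1 point.

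It would be wrong to infer bias or an invalid test: randomisation keeps the raw comparison unbiased. The primary proportional odds analysis is not affected.

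The size rests on the assumed ρ, d = 0.9, two-sided testing and complete data. The comparison with the mixed model also needs day to be categorical with a separate treatment main effect, which 9.3.3 does not spell out.

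**What to change.** In 9.3.3, state that the main comparison for each RAS component and biomarker models the day 4, 10 and 21 levels on arm, with the same analyte's day 1 level as a prespecified covariate. A longitudinal model that constrains the arms to a common day 1 mean is an equivalent choice. Use the log scale where suitable, and state a rule for zeros and values below detection. A log transform should not be imposed on every analyte, because the endpoints include counts. Keep the t-test or Wilcoxon as supportive, and say that the adjusted model takes precedence if the two disagree. Replace the conditional sentence on covariates with this named one.

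The cost is one degree of freedom per analyte and SAP wording, with no new participants or samples. A single covariate fits the limit that 9.3.1 sets.

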4.1.2 SECONDARY ENDPOINT

- Number of grade II or higher adverse events (AE) through day 21 of study
- Levels of various components of the RAS system including Ang(1-12), AngI, AngII and Ang(1-7)
- Levels of various blood biomarkers

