9 STATISTICAL CONSIDERATIONS

9.1 STATISTICAL HYPOTHESES

Primary hypothesis Maximum severity of disease, as assessed by the modified 7-point Clinical Status ordinal scale, will be less in the telmisartan arm compared to the placebo arm

Secondary hypotheses

- Telmisartan will be safe and well tolerated in symptomatic patients with COVID-19 over the 21 day study period
- Telmisartan will increase Ang(1-9), AngII and Ang(1-7); Elevated levels of these peptides in relation to angiotensin peptide receptors such as MasR, AT1R and AT2R expression will be important predictors of improved clinical outcomes
- Differences in biomarker levels will be seen between the 2 arms; Certain baseline values may predict clinical outcomes

Exploratory hypothesis:

- Loss of viral detectability will be faster in the telmisartan arm compared to the placebo arm

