9.3.2 ANALYSIS OF THE PRIMARY EFFICACY ENDPOINT(S)

The efficacy primary endpoint of the study is the maximum clinical severity of disease as assessed by the clinical status ordinal scale. The primary efficacy analysis will be performed using a proportional odds model. This model allows comparing odds ratios on ordinal categories between the experimental treatment and the placebo via a set of regression parameters. The statistical significance of regression parameters will be tested using a one-sided test for the superior efficacy by telmisartan. Alternatively, several ordinal categories can be combined to obtain a composite binary class outcome, in case of insufficient class representations observed. In this situation, group comparison with respect to a binary outcome can be performed using the logistic regression model.

In addition to the primary analysis, longitudinal outcomes obtained at baseline (day 1), days 4, 10, and 21 will be used in a generalized mixed-effect regression model (i.e., cumulative link mixed model) that contains treatment and days, and treatment: days interaction as fixed effects. In the model, treatment: days interaction represents the difference in longitudinal trajectories between the two treatment groups. The statistical significance of interactions will be determined. The regression models used for analysis can be further adjusted for any unbalanced covariates observed at baseline.

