9.3.4 SAFETY ANALYSES

The number of adverse events will be tabulated by grade and symptom/lab parameters. Proportions and corresponding 95% exact confidence intervals will be provided.

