9.4 SAMPLE SIZE

The sample size estimation for the proposed study is not provided considering that this is a pilot study. A total sample of 40 participants will be used in the study (20 per group). The above sample size was determined based on the feasibility assessment. Suppose, in the placebo group, the vector of probabilities for observing the ordinal scale outcomes is {0.40, 0.40, 0.05, 0.04, 0.04, 0.04, 0.03}, respectively for categories 1-7. If we assume the corresponding vector for the experimental treatment group as {0.76, 0.18, 0.02, 0.01, 0.01, 0.01}, that will produce an odds ratio of 5.0 between the two groups. In this scenario, we will have about 80% power to detect a treatment difference using the proportional odds model at 5% type-I error. Also, the selected sample size will allow us to detect a standardized effect size of 0.9 at Cohen's d scale, above 80% power, for a mean comparison between two groups via a two-sample T-test for a Gaussian outcome.

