9.5 MEASURES TO MINIMIZE BIAS

9.5.1 ENROLLMENT/ RANDOMIZATION/ MASKING PROCEDURES

After signing the Informed Consent Form (ICF), the subject is assigned a unique patient identifier number (PID). At the time of enrollment (randomization), the subject is assigned a unique subject identifier number (SID). PIDs and SIDs are not re-assigned. Screening Numbers and Subject Numbers are not re-assigned. Subjects are randomly allocated (1:1) to active medication (telmisartan) or placebo.

Randomization may occur after verbal informed consent has been obtained from the subject or representative, and subject eligibility has been confirmed. A study enrollment form will be sent to the research pharmacist to initiate the randomization process and assign the treatment to the participant. The research pharmacist will obtain the randomized treatment allocation from a computer-generated randomized treatment list for the subject and the pharmacist or designated staff will prepare the study medication. The study medication will not be provided to the participant however until a written informed consent is obtained. The site research staff and investigators (with the exception of the research pharmacist) will not have access to the treatment assignments and investigational drug products are over-encapsulated to blind the study drugs.

Since the research pharmacist is unblinded in order to provide the assigned treatment, the research pharmacist will not be involved with the assessment of outcomes or data capture except as necessary to manage drug distribution, control and accountability.

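### The only planned between-arm comparison of adverse events is a test of no difference; with 20 per arm a non-significant result cannot support 'safe and well tolerated', and no interval for the difference is named

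*Combined protocol and SAP*

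**What the plan says.** Safety and tolerability is the first-listed secondary objective (section 3). Section 9.1 turns it into a directional hypothesis, "Telmisartan will be safe and well tolerated in symptomatic patients with COVID-19 over the 21 day study period", with no margin or criterion attached. The endpoint in section 4.1.2 is a count: "Number of grade II or higher adverse events (AE) through day 21 of study".

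Four sections of the combined protocol and SAP bear on its analysis:

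- Section 9.3.3 summarises AEs by arm as frequencies and percentages and then compares the arms: "Chi-squared test or Fisher's exact test will be used to test for differences in proportions between two groups".
- Section 9.3.4 tabulates AEs by grade and by symptom or laboratory parameter, and adds: "Proportions and corresponding 95% exact confidence intervals will be provided".
- Section 9.3.1 promises 95% confidence intervals for efficacy and safety estimates. Its examples are averages and proportions.
- Section 9.3.5 reports study-drug discontinuation, withdrawal and loss to follow-up as proportions with exact intervals.

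None of them names a risk difference, risk ratio or other between-arm AE estimate with an interval. No AE rate, safety margin or power for the AE comparison is given.

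**The concern.** The hypothesis asserts the absence of a problem, while the only between-arm inference is a test whose null hypothesis is the absence of a difference. Such a test can produce evidence against the hypothesis. A non-significant result is not evidence for it, least of all at a sample size where non-significance is likely even under a sizeable excess of AEs.

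Separate intervals for each arm do not fill the gap, because they do not state how large an excess on telmisartan remains compatible with the data. Section 12.4.1 expects a favourable result to lead to grant applications for further telmisartan research, so a later reader will want that figure for safety as well as for efficacy.

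**Working it through.** **Inputs from the documents.** Section 9.4: "A total sample of 40 participants will be used in the study (20 per group"). Section 9.5.1: "Subjects are randomly allocated (1:1) to active medication (telmisartan) or placebo". Section 9.3.1: "Type-I error for hypothesis tests will be fixed at 5% nominal level". Section 9.3.2 makes the primary efficacy analysis one-sided ("tested using a one-sided test for the superior efficacy by telmisartan"). No sidedness is stated for AEs, so two-sided is assumed here and a one-sided variant is shown.

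**The plan's own power figures.** Section 9.4 gives power for efficacy only. A two-sample t-test with d = 0.9 and 20 per arm has 79.2% power two-sided by the noncentral t (81.2% by the normal approximation). An odds ratio of 5.0 gives 79.9% by simulation of the one-sided rank test. Both agree with the stated 80% or so. Neither says anything about AEs.

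**Power for the AE test.** Let X0 ~ Bin(20, p0) on placebo and X1 ~ Bin(20, p1) on telmisartan. Power = Σ P(X0 = i) P(X1 = j) over all pairs (i, j), among the 21 × 21 possible, with two-sided p ≤ 0.05. The placebo risk p0 is an assumption, so a range is shown.

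| Placebo to telmisartan risk | Fisher | Chi-squared, uncorrected |
|---|---|---|
| 10% to 20% | 7% | 14% |
| 20% to 40% | 19% | 29% |
| 30% to 60% | 35% | 46% |
| 35% to 70% | 47% | 59% |
| 40% to 80% | 65% | 75% |
| 45% to 90% | 84% | 91% |
| 40% to 60% (20-point excess, not a doubling) | 14% | 22% |

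One-sided Fisher power is 11%, 29% and 46% in the first three rows.

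As a concrete case, take 6/20 with an AE on placebo. Fisher's test gives p = 0.056 against 13/20 and falls below 0.05 only at 14/20. Uncorrected chi-squared gives p = 0.027 at 13/20 and p = 0.057 at 12/20, which is twice the placebo count.

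**Interval for the difference (Newcombe).** For each arm with observed proportion p, the Wilson limits are

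l, u = [p + z²/2n ± z√(p(1−p)/n + z²/4n²)] / (1 + z²/n), with n = 20 and z = 1.96.

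The upper limit for d = p1 − p0 is d + √((u1 − p1)² + (p0 − l0)²).

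- 4/20 in each arm: l = 0.081, u = 0.416. Upper limit = √(0.216² + 0.119²) = 0.247, so the interval is −25 to +25 points.
- 6/20 in each arm: l = 0.145, u = 0.519. Upper limit = √(0.219² + 0.155²) = 0.268, so the interval is −27 to +27 points.
- 6/20 on placebo and 12/20 on telmisartan: difference +30 points, interval −1 to +54, Fisher p = 0.11.

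With 4/20 in each arm the score interval for the risk ratio is 0.30 to 3.30, so even equal observed rates would not exclude a doubling.

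**The case against.** The plan is largely descriptive and already includes estimation. A reader might infer from section 9.3.3 that safety is examined only by a test. Sections 9.3.1, 9.3.4 and 9.3.5 show that it is not: AEs are tabulated by grade, proportions carry exact intervals, and discontinuations, which bear directly on tolerability, are reported with intervals and withdrawals with reasons. Those per-arm intervals already show imprecision (6/20 gives 12% to 54%), and anyone with the counts could derive the difference. All of this stands, and it limits the point to the between-arm comparison.

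A reader might also infer that the sponsor will report a p-value above 0.05 as proof of safety. No section says so or attaches a decision rule to the hypothesis. Section 9.3.7 describes a pilot looking for early evidence, and section 9.4 rests the sample size on feasibility.

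Finally, it is tempting to say that the test usually misses a doubling whatever the background rate. The documents give no such rate, and a high one is plausible. Participants are symptomatic at entry (section 5.1), worsening of a baseline condition counts as an AE (section 7.3), and grade 2 means interference with everyday activities (section 7.2.1). Power for a doubling passes 50% at a placebo risk of 35% with chi-squared, and between 35% and 37.5% with Fisher.

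What remains is that section 9.3.1 does not clearly cover a between-arm difference, since its examples are averages and proportions, and section 9.3.4 ties the AE intervals to proportions. Pilot status excuses low power. It does not make a null test the right between-arm summary.

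**Conclusion.** The point holds for the between-arm comparison. Its only stated form is a test of no difference, and no risk difference or ratio with an interval is named. For an assumed placebo risk of 30% or less, two-sided power to detect a doubling is below one half with either permitted test. Above about 35% a doubling becomes detectable more often than not, but it is then an excess of 35 points or more; for a 20-point excess from 40%, power is still only 14% (Fisher) or 22% (chi-squared). The interval result depends less on the background rate: equal observed counts of 4/20 or 6/20 leave an excess of about 25 to 27 points unexcluded.

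These figures assume 20 analysed participants per arm, one yes/no outcome per participant, and two-sided 5% testing. They show that non-significance could not support the hypothesis in section 9.1. They do not show that telmisartan is unsafe, or that the sponsor intends to claim safety from a p-value. This is an inexpensive improvement to the analysis plan, not a flaw in the design.

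**What to change.** In sections 9.3.3 and 9.3.4:

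1. Name as the main between-arm safety result the difference, telmisartan minus placebo, in the proportion of participants with at least one grade II or higher AE through day 21, with a 95% interval (Newcombe or Miettinen-Nurminen). This also settles the unit of analysis, since section 4.1.2 counts events while section 9.3.3 compares proportions. The event count can stay in the tabulation.
2. Report the upper limit in words, as the largest excess that the data cannot exclude.
3. Label the chi-squared or Fisher test as descriptive, state whether it is one- or two-sided, and say that the conclusion on safety and tolerability will not rest on non-significance.

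This needs no new data, participants or procedures. It costs a few sentences in the plan and one extra line in the safety table. The drawback is that the interval will look wide, which is a fair picture of what 20 per arm can show.
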